## 2. Prevention of CIAKI

Renal injury resulting from iodinated contrast is potentially preventable. Procedures that utilize intravascular contrast are usually scheduled in advance, providing sufficient time to implement preventive measures. Moreover, patients at increased risk for CIAKI are easily identifiable by the presence of known clinical risk factors. Past efforts to find effective preventive strategies for CIAKI have focused on four principal approaches: 1) use of less nephrotoxic contrast agents; 2) provision of pre-emptive renal replacement therapy to remove contrast from the circulation; 3) utilization of pharmacologic agents to counteract the nephrotoxic effects of contrast media; and 4) expansion of the intravascular space and enhanced diuresis with IV fluids.

Over the past 25 years, there has been considerable progress in developing less nephrotoxic contrast agents. In the late 1980s, low-osmolal contrast replaced the considerably more nephrotoxic high-osmolal agents, resulting in a decreased incidence of CIAKI. Over the past decade, several trials have compared the renal effects of iso-osmolal and low-osmolal contrast media. While these studies have yielded conflicting data regarding the relative risks of CIAKI with low versus iso-osmolal contrast media, it is clear that the incidence of CIAKI remains substantial in high-risk patients despite the use of these less nephrotoxic agents.

Renal replacement therapies for the prevention of CIAKI have been largely ineffective, and in some instances, “prophylactic” hemodialysis has been associated with harm. The interpretation of studies of hemofiltration for the prevention of CIAKI has been confounded by the use of change in SCr, a variable that is directly impacted by hemofiltration, as the primary study endpoint. As a result, use of dialysis or hemofiltration to prevent CIAKI is not currently recommended.

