| Assessment of 1  outcome                                  |                           |                   |                                       |                                    |                         |                           |                             | X                        |                         |
| Assessment of 2  outcomes                                 |                           |                   |                                       |                                    | X f          |                           |                             | X                        |                         |
| Assessment of ESRD  |                           |                   |                                       |                                    |                         |                           |                             |                          | X                       |
| Assessment of long-term mortality                                     |                           |                   |                                       |                                    |                         |                           |                             |                          | X                       |

a denotes labs or procedures performed as part of routine clinical care by providers within 30 days prior to angiography

b eligibility based on eGFR calculated from SCr performed as part of routine clinical care within 30 days prior to angiography. If no Scr measurement was taken within 30 days prior to angiography, the patient’s consent will be sought and if obtained, a blood sample will be drawn for Scr measurement at the site’s VA laboratory to determine eligibility.

c blood pressure denotes measurement taken as part of routine clinical care within 3 days prior to angiography; weight is most recent weight in medical record or by patient report or coordinator measurement

d denotes SCr sent to central study laboratory for endpoint ascertainment

e denotes information collected on subjects who remain hospitalized following angiography or who return to the hospital within 4 days of angiography

f denotes assessment of CIAKI based on 4-day study SCr

g denotes labs performed as part of routine clinical care by providers within 1 year prior to angiography

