*d. Justification for 90-day time frame to assess the primary endpoint*

We chose to assess our primary endpoint at 90 days following angiography for two reasons. First, this represents a period of time during which adverse outcomes are more likely than not to be associated with the index angiographic procedure. Second, 90 days is commonly used in clinical practice and is proposed by the Kidney Disease: Improving Global Outcomes Foundation and the National Kidney Foundation to define the transition between acute and chronic impairment in kidney function. Therefore, persistent decline in kidney function measured at 90-days after the index angiographic procedure likely represents irreversible renal damage.

4. Secondary study outcomes

The secondary outcomes consist of:

- CIAKI defined by an increase in SCr of  $\geq 0.5$  mg/dL and/or  $\geq 25\%$  from the pre-procedure value at 4 days following angiography.
- Death within 90 days of the index angiographic procedure.

- The renal components of the primary endpoint:
  - Need for acute dialysis within 90 days of the index angiographic procedure
  - Persistent decline in kidney function at 90 days following the index angiographic procedure
- Hospitalization with acute coronary syndrome, heart failure, or cerebrovascular accident within 90 days following the index angiographic procedure. These outcomes will be defined as a primary or secondary discharge diagnosis of acute coronary syndrome (i.e., STEMI, NSTEMI, unstable angina), heart failure, or cerebrovascular accident documented in the VA electronic medical record or the hospital discharge summary obtained for non-VA hospitalizations. (This will include the occurrence of any of these events during the index hospitalization).
- All-cause re-hospitalization within 90 days of the index angiographic procedure assessed as episodes of re-hospitalization, days of hospitalization (inclusive of the index hospitalization), and hospital free days (alive and not in the hospital) through day 90.

Because AKI can occur following angiography for reasons unrelated to the administration of iodinated contrast, in a sensitivity analyses, we will also evaluate the development of CIAKI using the same threshold change in SCr, but excluding patients who experienced hypotension and/or who underwent cardiac surgery or non-cardiac vascular surgery within the 4 days following angiography.

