#### 7. 4 day blood collection

Participants discharged from the hospital within four days following angiography will be asked

to provide a blood sample 4 ( $\pm$ 1) days following the angiogram. Options for this blood draw may include, but not be limited to: 1) returning to the study VA; 2) having a mobile phlebotomy service draw the blood; or 3) having the blood drawn at a non-study VA site such as a Community-Based Outpatient Clinic (CBOC) or another VA facility closer to the participant’s home.

We chose this time frame to assess post-procedure renal function as almost all patients who develop CIAKI have an elevated SCr within 4 days. One aliquot of this sample will be sent to the central study laboratory to assess the development of CIAKI. A second aliquot from this sample will be delivered to the nearest VA laboratory in order for the practitioner who performed the angiogram to ascertain whether the patient experienced a rise in SCr. This approach will obviate the need for the patient to have more than one blood draw to assess for the development of CIAKI for study and clinical purposes. For patients who remain hospitalized for at least 4 ( $\pm$ 1) days following angiography, a blood sample will be drawn at 4 ( $\pm$ 1) days post-procedure. One aliquot of this sample will be sent to the central study laboratory for subsequent analysis for the development of CIAKI, while a second aliquot will be delivered to the hospital laboratory for the primary provider to review whether the patient experienced a post-procedure rise in SCr.

To ensure patient safety and assist providers, research personnel will notify the provider who performed the angiography that a 4 ( $\pm$ 1) days SCr will be processed in the VA laboratory as part of the study and will send an encrypted email to the patients’ primary provider describing the results of this 4 ( $\pm$ 1) days post-procedure SCr within 2 days of the completion of this test.

Since this creatinine determination is part of the secondary end-point, it is very important that the blood collection be done at 4 ( $\pm$ 1) days after angiography. We recognize that unforeseen circumstances may preclude collection within this window. Under such circumstances the blood should be collected as soon as possible and most proximate to 5 calendar days after the date of angiography. In the event the blood is obtained before 3 or after 5 days following angiography, a protocol deviation should be completed.

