We recommend that this contact should be made at 35 days after angiography, with an allowable range of 35-49 days. We recognize that sometimes it may be difficult to schedule a patient within this window. However, it is important to collect the required data, which should be done even if done after the recommended time frame has elapsed. It will not be considered a protocol deviation as long as the required data are collected and there is progress note documenting the attempt to schedule the data collection during the recommended time frame.

10. Day 90 post procedure assessment

(90 days post angiography, allowable range 90-104 days post angiography)

*a. 90 day blood collection*

In advance of the patient's 90 day assessment, they will be contacted by research personnel regarding their 90 day blood collection. The blood sample obtained will be sent to the Central Laboratory for Scr measurement. Patients who are willing and able will return to the study VA at which their angiogram took place 90 days (allowable range of 90-104 days) following their index angiogram to provide this blood sample. Other options for this blood draw may include, but not be limited to: 1) having a mobile phlebotomy service draw the blood; or 2) having the blood drawn at a non-study VA site such as a Community-Based Outpatient Clinic (CBOC) or another VA facility closer to the participant's home.

If a participant initiates renal replacement therapy (intermittent hemodialysis, peritoneal dialysis, continuous renal replacement therapy [CRRT], or prolonged intermittent renal replacement therapy [PIRRT]) within 90 days of the index procedure, the study coordinator will collect the 90-day blood draw based on the following criteria:

- If the participant initiates renal replacement therapy within 90 days of the index angiography procedure and continues to require renal replacement therapy on or after day 90, the 90-day blood draw will not need to be collected
- If the participant initiates renal replacement therapy within 90 days of the index angiography procedure but recovers kidney function and renal replacement therapy is discontinued prior to day 90, the participant should have his/her 90-day blood drawn

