
## **F. Assessment of secondary outcomes**

### **1. Assessment of CIAKI**

Most patients who develop CIAKI manifest an initial increase in SCr within 2 to 4 days following contrast administration. However, past studies demonstrate that some patients who develop CIAKI may not be identified by a single SCr assessment at 48 hours. The optimal timing of assessment of SCr following the index angiogram to assess for the development of CIAKI in our trial was carefully considered by the planning committee. While it was agreed that multiple SCr assessments (e.g., at 2 days and 4 days) would ensure the identification of all patients who developed CIAKI, we ultimately determined that a single assessment at 4 days following angiography was optimal for several reasons. First, almost all patients who develop CIAKI will manifest an increase in SCr at 4 days following angiography. Second, an increase in SCr at 4 days following angiography is more likely to represent clinically significant CIAKI than an increase in SCr at 48 hours, as early changes in SCr are more likely to reflect transient hemodynamically-mediated perturbations in SCr rather than clinically consequential renal injury. Finally, the planning committee did not feel that measuring SCr at multiple time points in order to identify a small number of additional patients who meet criteria for this secondary outcome justified the added cost of more than \$350,000 for each additional SCr assessment.

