3.5.2. Secondary Endpoints

The secondary endpoints **except for CIAKI** for the study are assessed at 90 days post index procedure and they include the following individual outcomes:

(1) CIAKI defined by an increase in SCr of ≥ 0.5 mg/dL and/or $\geq 25\%$ increase at 96 hours following contrast administration, derived as follows.

$$(\text{SCr}_{96\text{Hours}} / \text{Scr pre-procedure}) * 100\% \geq 125\%$$

(2) Death from all causes to be verified by medical record and/or vital status registry documentation such as the VA Beneficiary Identification and Records Locator System, the National Center for Health Statistics National Death Index database, the Social Security Administration's Death master File.

(3) MAKE defined by (a) initiation of any modality of renal replacement therapy, which include intermittent hemodialysis, peritoneal dialysis, continuous renal replacement therapy, or prolonged intermittent renal replacement therapy, or (b) persistent decline in kidney function as defined in **3.5.1**.

(4) Hospitalization with acute coronary syndrome, heart failure, or cerebrovascular accident within 90 days following the index angiographic procedure. These outcomes will be defined as a primary or secondary discharge diagnosis of acute coronary syndrome (i.e., STEMI, NSTEMI, unstable angina), heart failure, or cerebrovascular accident documented in the VA electronic medical record or the hospital discharge summary obtained for non-VA hospitalizations. Note: This will include the occurrence of any of these events during the index hospitalization.

(5) All-cause re-hospitalization within 90 days of the index angiographic procedure assessed as episodes of re-hospitalization, days of hospitalization (inclusive of the index hospitalization), and hospital free days (alive and not in the hospital) through day 90.

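### CIAKI is scored from the day-4 creatinine alone, with no rule for patients who start renal replacement therapy before that sample

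*Protocol*

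**What the plan says.** Protocol VII.G.4 measures the CIAKI rise "from the pre-procedure value at 4 days following angiography". Table 6, footnote f, confirms the source: it "denotes assessment of CIAKI based on 4-day study SCr". Section VIII.F.1 explains that there is only one measurement: "we ultimately determined that a single assessment at 4 days following angiography was optimal for several reasons". Section VII.H.7 sets the window at 4 (±1) days ("In the event the blood is obtained before 3 or after 5 days following angiography, a protocol deviation should be completed") and has the sample drawn on patients still in hospital, with no exception for dialysis. SAP 3.5.2(1) gives the same thresholds "at 96 hours following contrast administration, derived as follows", and the formula it prints uses only the creatinine ratio.

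The planned CIAKI sensitivity analyses exclude patients with hypotension or surgery (VII.G.4) or another documented cause of kidney injury (VIII.A.1). Neither addresses RRT.

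The protocol recognises elsewhere that RRT changes creatinine. Section III.B.2 says the hemofiltration studies were "confounded by the use of change in SCr, a variable that is directly impacted by hemofiltration". For the day-90 sample, VII.H.10.a provides that if a patient "continues to require renal replacement therapy on or after day 90, the 90-day blood draw will not need to be collected". The day-4 sample has no counterpart.

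**The concern.** Dialysis lowers creatinine. A patient injured severely enough to be dialysed on day 2 or 3 can therefore have a day-4 value near baseline, and the rule as written then scores no CIAKI. If the sample is not drawn, SAP 5.1 does not impute missing endpoints and excludes the patient. SAP 5.4 carries the primary strategy over to the secondary outcomes, so the same handling would apply here.

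Two uses of CIAKI are exposed. First, it is called a key secondary endpoint (III.A.2.e; VIII.A.2), and Protocol II.A hypothesises that benefit is mediated by less CIAKI within 4 days. A patient who crosses the threshold on day 2 fits that hypothesis but may not fit the day-4 score. Second, CIAKI status defines the strata for the pathway analysis in XVII.E. Every patient missed in this way has a MAKE-D event, because dialysis is a component of MAKE-D. The error therefore moves events specifically into the no-CIAKI stratum and is not random noise.

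**Working it through.** No planned sample size, power or alpha depends on this rule, so there is no document figure to reproduce. The check has four steps.

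**1. Can the rule misscore a patient?** Take an invented baseline of 3.0 mg/dL, rising to 5.5 on day 2, then dialysis, then 3.2 on day 4. The difference is 3.2 − 3.0 = 0.2 mg/dL and the ratio is 3.2/3.0 = 1.07. Both thresholds are missed, so the score is no CIAKI. With a day-4 value of 3.5 the difference is 0.5 and the patient counts. Misscoring therefore needs RRT before the sample, a sample drawn, and a value below both thresholds.

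**2. How many cases?** Inputs from the documents: N = 7,680; CIAKI in 8.5% (coronary) and 13.2% (non-coronary) of clinically stable patients having non-urgent procedures (III.A.1). Assumptions, since the documents give neither figure: 0.1% to 1% of patients dialysed before the sample, and 50% to 100% of those below threshold.

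- Dialysed early: 0.001 × 7,680 = 7.7; 0.01 × 7,680 = 76.8.
- Missed, low end: 7.7 × 0.5 = 3.8. High end: 76.8 × 1.0 = 76.8.
- Share of CIAKI missed = (early rate × share below threshold) / CIAKI rate.

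| CIAKI rate | Low end | High end |
|---|---|---|
| 8.5% | 0.0005/0.085 = 0.6% | 0.01/0.085 = 11.8% |
| 13.2% | 0.0005/0.132 = 0.4% | 0.01/0.132 = 7.6% |

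For scale, XVII.A.2 reports that 5% started dialysis by day 90 in the VA database, or 0.05 × 7,680 = 384. The assumed 8 to 77 is then 2% to 20% of those starts.

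**3. Effect on the CIAKI to MAKE-D association.** Take an overall MAKE-D rate of 7.6% (584 events), CIAKI at (2/3) × 8.5% + (1/3) × 13.2% = 10.1% (about 773 patients; VIII.B.1 puts non-coronary procedures at about one third), and a true risk ratio of 4, which XVII.E reports approximately.

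- Risk without CIAKI: 584 / (4 × 773 + 6,907) = 5.84%. This gives about 181 events among 773 patients with CIAKI and 403 among 6,907 without.
- Moving 4 patients, all with events: (177/769) / (407/6,911) ≈ 3.9.
- Moving 38: (143/735) / (441/6,945) ≈ 3.1.
- Moving 77: (104/696) / (480/6,984) ≈ 2.2. This end is extreme, since 77 would be over 40% of the 181 events.

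**4. Effect on the treatment comparison for CIAKI.** If missed cases are proportional across arms, a true risk ratio of 0.75 stays at 0.75. If 1% of control and no treated patients were missed, it would appear as 0.06375/0.075 = 0.85 (8.5% CIAKI) or 0.099/0.122 = 0.81 (13.2%), closer to no effect.

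**The case against.** The strongest reply is that this is a narrow gap of unknown and probably small frequency. The definition is deliberately sensitive, and a dialysed patient may still exceed one of its thresholds. Many tabulated trials report dialysis in 0% to 2%, and the largest NAC trial (2,308 patients) reports 0.3%, although the protocol notes that most of its patients were at minimal renal risk. These patients are not lost as renal events: RRT counts in MAKE-D, in secondary MAKE and as an exploratory component. The CIAKI-stratified analysis is itself exploratory. All of this stands, and it limits the size of the problem without supplying the missing rule.

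The two parallels in the protocol should also not be pressed too far. In the hemofiltration studies RRT was the treatment under test, so it altered creatinine by arm; here it is an uncommon event under blinded allocation. The day-90 provision says when blood need not be drawn. It is not a scoring rule, so a reader should not infer that a matching scoring rule for day 4 was forgotten.

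Finally, counting all early RRT as CIAKI would include some RRT started for reasons other than contrast injury, and would depart from the definition kept for comparability with earlier trials. That is a fair cost, and a creatinine-only sensitivity analysis meets it.

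**Conclusion.** The gap is real: applied as written, the rule can score a dialysis-requiring injury as no CIAKI, or drop it. Under the stated assumptions about 4 to 77 cases are missed, roughly 0.4% to 12% of CIAKI, and the CIAKI to MAKE-D association is biased toward the null. The effect on the treatment comparison depends on how early dialysis is split between arms and may be nil.

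A reader might infer that all of the most severe cases are misclassified. The documents do not support that. Patients dialysed after the sample are unaffected, some dialysed earlier will still meet a threshold, and no rate of dialysis before day 4 is given. Nor does the point touch the primary endpoint, its power or its alpha.

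**What to change.** In Protocol VII.G.4 and XVII.C and in SAP 3.5.2(1), state that RRT initiated after angiography and on or before the date of the 4-day sample, or by day 5 if no sample is drawn, is scored as CIAKI whatever the 4-day creatinine. Keep the creatinine-only definition as a sensitivity analysis.

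The data are already planned. VII.H.6 records RRT use for patients in hospital or readmitted within 4 days, VII.H.8 asks about starting dialysis at the day-5 contact, and VII.H.10.b records the RRT initiation date. The derivation should use that date, because the VII.H.6 item lists none. No clock time is listed, which is why the rule is worded by date.

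The cost is one sentence in each of three places, a line of derivation code and one extra analysis. The downside is that a few cases are classed by treatment received rather than by creatinine. The rule concerns scoring only and changes no patient care.

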## VI. STUDY POPULATION AND PATIENT RECRUITMENT

### A. Study population

The study population will consist of outpatients and inpatients undergoing coronary or non-coronary angiography at any of the study sites who are at high risk for the development of CIAKI and its serious, adverse medical outcomes. Since a major risk factor for CIAKI and subsequent adverse clinical events following angiography is the presence of decreased kidney function, and at any given level of kidney function the risk is increased in patients with diabetes mellitus, we will enroll patients with an estimated glomerular filtration rate (eGFR)  $<60$  mL/min/1.73 m^2 who have diabetes mellitus, as well as patients who have an eGFR  $<45$  mL/min/1.73 m^2 regardless of whether or not they have diabetes mellitus. To optimize the recruitment of patients at particularly high risk for adverse events following angiography, we will include patients undergoing urgent procedures and those with non-decompensated heart failure (i.e., heart failure that is not being treated with inamrinone, milrinone, dobutamine or nesiritide, isolated ultrafiltration therapy, and/or an intra-aortic balloon pump) at the time of their procedure.

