## **B. Screening and patient recruitment**

Requisite waivers of HIPAA authorization and informed consent for screening will be obtained in order to allow study coordinators to review angiography logs/schedules in advance to identify patients scheduled for coronary or non-coronary angiography and assess their electronic medical records for eligibility. After the study is introduced to the patient by an individual participating in their care, research personnel will contact potentially eligible subjects to describe the study and complete the screening process.

Based on our past study of Veterans undergoing angiography and recent queries of VA clinical sites nationwide, more than 90% of patients will have had a SCr measured as part of routine care within 30 days prior to angiography. For the small number of patients who have not had a SCr measured within 30 days, research personnel will contact them as stated above and, if they are agreeable, administer informed consent and then obtain a screening SCr prior to angiography to assess eligibility based on their underlying level of kidney function.

We will require that potentially eligible female subjects who are able to have children (not considered post-menopausal [had a menstrual period within previous 12 months], not had tubal ligation, a hysterectomy or bilateral oophorectomy) and are sexually active, have a negative pregnancy test before being enrolled in the study.

We believe that even for urgent angiograms for indications such as non-ST elevation MI or peripheral vascular occlusion, there will be sufficient time (>3 hours) prior to the procedure to determine eligibility, obtain consent, perform randomization, and implement the study interventions. Including these subjects will help ensure the recruitment of a high-risk patient

population. No adult patient (age  $\geq 18$  years) will be excluded from participating based on age, gender, race, ethnicity, or sexual preference.

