### **C. Secondary end-points**

Our secondary objectives, as previously outlined, will be tested using a logistic regression analysis similar to the primary objective. These objectives are:

1. To assess the effectiveness of the interventions to prevent CIAKI, defined by an increase in SCr of  $\geq 0.5$  mg/dL and/or  $\geq 25\%$  at 96 hrs following angiography compared to baseline values.
2. To assess the effectiveness of the interventions for the prevention of the following outcomes within 90 days of coronary or non-coronary angiography:
  - a) death
  - b) major adverse kidney endpoints (MAKE) including need for acute dialysis or persistent decline in kidney function defined by an increase in SCr of at least 50% at 90 days
  - c) hospitalization with acute coronary syndrome, heart failure, or cerebrovascular accident defined by primary or secondary ICD-9 discharge diagnosis codes of acute coronary syndrome (i.e., STEMI, NSTEMI, unstable angina), heart failure, or cerebrovascular accident and/or by documentation of any of these three events in the hospital discharge summary.
  - d) all-cause hospitalization

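### The secondary cardiovascular hospitalization endpoint has no onset rule for the index stay, so disease present before randomization can be scored as an outcome

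*Protocol*

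**What the plan says.** The endpoint is defined in three places.

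- **Protocol VII.G.4.** The outcome is "Hospitalization with acute coronary syndrome, heart failure, or cerebrovascular accident within 90 days following the index angiographic procedure". The operational criterion follows: "These outcomes will be defined as a primary or secondary discharge diagnosis of acute coronary syndrome", with HF and CVA treated the same way. A parenthesis adds: "This will include the occurrence of any of these events during the index hospitalization".
- **SAP 3.5.2(4).** The same definition, with the same addition: "Note: This will include the occurrence of any of these events during the index hospitalization".
- **Protocol XVII.C, item 2c.** This is wider. It accepts ICD-9 discharge codes "and/or by documentation of any of these three events in the hospital discharge summary", and it does not mention the index stay.

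The entry population overlaps with these diagnoses. Protocol VI.A states: "The study population will consist of outpatients and inpatients undergoing coronary or non-coronary angiography". To raise risk, it adds: "we will include patients undergoing urgent procedures and those with non-decompensated heart failure". HF is excluded only when one of the listed therapies is in use at the time of angiography. Protocol VI.B expects enough time for enrolment "even for urgent angiograms for indications such as non-ST elevation MI or peripheral vascular occlusion", and NSTEMI is itself a listed component of the endpoint.

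SAP 5.4 tests each secondary endpoint as a binary outcome by odds ratio at p=0.025. Protocol XVII.E item 5 also analyses ACS, HF and CVA separately as exploratory outcomes.

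**The concern.** A discharge diagnosis describes the whole stay and carries no onset date. If the index stay counts and the criterion is a discharge diagnosis, a patient admitted with NSTEMI, randomized, given an uneventful angiogram and discharged with that diagnosis meets the endpoint. So does an inpatient whose existing HF is a secondary diagnosis on the index discharge record.

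Neither bicarbonate nor NAC can prevent a condition that came first. Such events carry no information about treatment, but they enter both numerators. A null result could then not be read as absence of a cardiovascular effect, and the reported 90-day incidence would be too high in every arm. Protocol VIII.D already gives masking by events independent of the interventions as a reason for keeping cardiovascular events out of the primary endpoint. The index-stay rule adds more events of that kind to the secondary one.

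**Working it through.** **Step 1. Does any rule restrict index-stay events to those that begin after angiography?**

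| Place | What it provides | Does it separate new from presenting disease? |
|---|---|---|
| Protocol VII.G.4, SAP 3.5.2(4) | Window of 90 days after the procedure; discharge diagnosis; index stay included | The window hints at it; the criterion does not apply it |
| Protocol XVII.C 2c | Codes and/or discharge-summary documentation | No |
| Protocol VII.H.10.b (90-day assessment) | Hospitalization date and discharge diagnoses | No event onset date |
| Protocol VII.H.3 | Indication for coronary angiography | Collected, not used in the endpoint |
| Protocol VII.H.1 | Inpatient or outpatient status before the procedure | Collected, not used in the endpoint |
| Protocol VII.H.6 | Dated MI from 12 hours to 4 days | MI only, in that window, not linked to the endpoint |
| Protocol VIII.F (cardiovascular outcomes) | Discharge-summary review; fuller adjudication declined | No |

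No rule does so.

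**Step 2. Size.** The documents state no event rate, effect or power for this endpoint, so there is no figure to reproduce. Inputs:

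- From the documents: 7,680 patients, 3% loss and two-sided alpha 0.025. Evaluable patients per factorial margin: 7,680 × 0.97 / 2 ≈ 3,725.
- Borrowed: RR = 0.75, which Protocol XVII.A postulates for MAKE-D only.
- Assumed: *p*, the true post-procedure control rate in patients without a qualifying index diagnosis, and *q*, the share of patients who already have one.

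Formulas:

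- control rate c = q + (1 − q)p
- treated rate t = q + (1 − q)(0.75p)
- OR = [t/(1 − t)] / [c/(1 − c)]
- share of control events already present before randomization = q/c
- power from the normal approximation for two proportions, n per margin: Φ{[(c − t)√n − 2.241√(2m(1 − m))] / √(c(1 − c) + t(1 − t))}, with m = (c + t)/2

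As a check on the power formula, the MAKE-D rates of 8.70% and 6.52% give 90.5%, against the stated 90%.

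Example, p = 10% and q = 20%: c = 0.20 + 0.80 × 0.10 = 0.280 and t = 0.20 + 0.80 × 0.075 = 0.260. OR = (0.260/0.740)/(0.280/0.720) = 0.351/0.389 = 0.90. Share present before randomization = 0.20/0.28 = 71%.

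| q (p = 10%) | c | t | RR | OR | Share of control events pre-existing | Power |
|---|---|---|---|---|---|---|
| 0 | 10.0% | 7.50% | 0.75 | 0.73 | 0% | 94% |
| 10% | 19.0% | 16.75% | 0.88 | 0.86 | 53% | 62% |
| 20% | 28.0% | 26.0% | 0.93 | 0.90 | 71% | 38% |
| 40% | 46.0% | 44.5% | 0.97 | 0.94 | 87% | 17% |

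The OR is the planned measure (SAP 5.4); the RR is shown for orientation.

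**Step 3. Sensitivity to p, at q = 20%.** With p = 5%, the OR moves from 0.74 to 0.95 and power falls from 65% to 11%. With p = 15%, the OR moves from 0.72 to 0.87 and power falls from 99.5% to 72%.

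**The case against.** The strongest reply is that the definition already contains its own limit. It speaks of hospitalization within 90 days following the procedure, and the added sentence speaks of events occurring during the index stay. Together these can mean that a new post-procedure event before discharge counts as well as a readmission. That would be sensible, since Protocol VIII.C.2 expects some volume overload or pulmonary edema around the procedure. This reading may well be what the authors meant, so a reader who infers that presenting disease is counted by design goes further than the text allows. The objection does not remove the problem. The criterion that will be applied is a whole-stay diagnosis, and nothing in the data collection or analysis turns the apparent intent into a rule.

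Several limits do stand.

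- A reader might infer that the main result is compromised or that one arm is favoured. Neither follows. This is one of five secondary endpoints, MAKE-D is untouched, and randomization should balance pre-existing disease. The harm is dilution.
- A large share such as 40% has no support in the documents. Outpatients without an index stay cannot qualify through it, about one-third of VA procedures are non-coronary (Protocol VIII.B.1), and nearly all procedures are described as non-emergent and scheduled (Protocol IX).
- It is tempting to say that the data to fix this already exist. They do so only in part: no dated onset is listed for in-stay HF or CVA, or for MI outside 12 hours to 4 days.
- Chronic HF listed on a later admission also qualifies. Requiring HF to be the reason for that admission would be partly a preference for a narrower endpoint, not the correction of an error.
- Protocol VIII.F openly acknowledges the limits of record-based ascertainment, though it does not address the index stay.

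**Conclusion.** The point holds as a gap between apparent intent and operational rule. As written, the three definitions let an ACS, HF or CVA diagnosis that came before randomization count as an outcome when it appears on the index discharge record. The expected effects are an odds ratio nearer to 1, less power for a formally tested secondary endpoint and its component analyses, and an inflated 90-day rate.

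Confidence is high that the rule is missing and low about the size. The illustrative odds ratios of about 0.86, 0.90 and 0.94, against a true 0.73, rest on an assumed 10% control rate, assumed index-diagnosis shares of 10%, 20% and 40%, and a 25% reduction that the documents postulate only for MAKE-D. Severity is moderate: the endpoint is secondary and the primary conclusions do not depend on it.

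**What to change.** Align Protocol VII.G.4, Protocol XVII.C item 2c and SAP 3.5.2(4) on one definition:

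1. An index-stay diagnosis of ACS, HF or CVA counts only if the discharge summary documents onset after the index angiogram and the diagnosis is neither the presenting diagnosis nor the indication for angiography.
2. Where onset cannot be established, count only admissions that begin after index discharge, using the hospitalization dates and discharge diagnoses already collected.
3. Report the present any-diagnosis definition as a sensitivity analysis.
4. Apply the same rule to the component analyses in Protocol XVII.E item 5.

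The change should be made before treatment codes are broken, so that it cannot be seen as driven by results.

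The cost is wording in both documents and an onset or present-on-admission check added to the planned discharge-summary review. That check is new work and needs some judgement, because dated onset is now collected only for MI from 12 hours to 4 days. Fewer events will be counted, and some true in-stay events with undocumented onset will be missed.
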